8.7.2.2. Anchor Based Approach to Find Clinically Meaningful Change

Estimation of meaningful change is achieved by computing the change scores for the EORTC-QLQ-C30 and EORTC-QLQ-BIL21 scores between baseline and follow-up associated with minimal improvement groups defined on PGI-C and change from baseline to post-baseline PGI-S ($\Delta\text{PGI-S}$) ratings as anchors. This approach will be taken for only before-crossover data. Minimally sufficient improvement is directly defined from the PGI-C by analyzing those subjects who report a minimal level of improvement on the anchors. Minimally sufficient improvement for the PGI-S is operationalized by taking the difference in PGI-S between baseline and follow-up and selecting participants with a one-point improvement. Average EORTC-QLQ-C30 and EORTC-QLQ-BIL21 scores will be computed for each of the anchor-based minimally sufficient improvement group definitions.

Relevant subscales of the EORTC-QLQ-C30 and EORTC-QLQ-BIL21 will be paired with their most-appropriate PGI-C/PGI-S rating (eg, the physical functioning PGI-C/S will be employed for the EORTC-QLQ-C30 physical function subscale). Similarly, the EORTC-QLQ-C30 appetite item and EORTC-QLQ-BIL21 eating symptoms subscale will be paired with the appetite PGI-C/S. Finally, the EORTC-QLQ-C30 and EORTC-QLQ-BIL21 pain subscales will each be paired with the PGI-C/S as anchors.

EORTC-QLQ-C30 and EORTC-QLQ-BIL21 change scores will be plotted as cumulative distribution functions (CDFs) for change. Cumulative distribution functions will be stratified on their respective anchor variables (PGI-C and $\Delta\text{PGI-S}$). In addition, after unblinding, the CDFs will be stratified by treatment-arm.

8.7.2.3. EQ-5D-5L Analysis

The EQ-5D contains a descriptive system with one response for each of 5 dimensions (Mobility, Self-Care, Usual Activities, Pain/Discomfort, and Anxiety/Depression). The first response is coded as 1 (indicating no problems), the second response is coded as a 2 (indicating slight problems), the third response is coded as a 3 (indicating moderate problems), the fourth response is coded as a 4 (indicating severe problems), and the fifth response is coded as a 5 (indicating unable to function). Ambiguous responses (eg, more than one response in a dimension) are treated as missing values. For each dimension, the number and percentage of subjects in each category will be summarized by treatment and visits.

The EQ-5D-5L also contains a utility scale of health state (VAS) ranging between 0 (worst health) and 100 (best health). Summary statistics for VAS scores and the absolute change from baseline will be reported by treatment and visits.

8.8. Post Crossover

Upon the radiographic progression of disease, subjects will be unblinded. If it's determined that they received placebo, subjects will be allowed to cross over to AG-120, provided they continue to be eligible for the study. Data after crossover will be analyzed separately, but in a similar fashion as outlined above.

In particular, tumor assessments after crossover will be based on Investigator assessment. Tumor measurements will be re-baselined prior to the start of crossover. The corresponding endpoints include:

- PFS per Investigator assessment (PFS2)
- Objective response rate /best overall response per Investigator assessment. Note that SD<38 days of the first AG-120 dose date will be assigned as UNK.
- Time To Response and DOR per Investigator assessment

9. SAFETY ANALYSIS

Unless specified otherwise, the safety data will be summarized by treatment based on SAS. Specifically, it will include placebo before crossover, AG-120 as dosed, AG-120 after crossover, and total AG-120. The total AG-120 includes all the subjects who have ever been dosed with AG-120 (that is, the sum of AG-120 as dosed and AG-120 after crossover). If a subject receives at least one dose of AG-120, the actual arm will be AG-120 as dosed. The same rule applies to the after crossover.

9.1. Adverse Events

Treatment emergent adverse events (TEAEs) are defined as any AEs that begin or worsen on or after the start of study drug through 28 days after the last dose of study drug. All AEs will be coded using the Medical Dictionary for Regulatory Activities (MedDRA) dictionary, unless otherwise specified. The severity will be graded based on the NCI CTCAE. All AEs will be listed. Only TEAEs will be summarized and will be referred to as AEs hereafter.

If a subject experiences multiple AEs under the same PT within an SOC, then the subject will be counted only once for that PT within that SOC. If a subject experiences the same AE more than once with different intensity or grade, then the event with the highest grade will be tabulated in “by grade” tables.

Tables summarizing the incidence of AEs will be generated by treatment arms for each of the following:

- Overall summary of AEs
- All AEs by SOC and PT
- Most common AEs by PT (ie, those events reported by $\geq 5\%$ of subjects in any treatment group)
- Most common Treatment-Related AEs by PT (ie, those events reported by $\geq 5\%$ of subjects in any treatment group)
- Grade 3 or higher AEs by SOC and PT
- Most common Grade 3 or higher AEs by PT (ie, those Grade 3 or higher AEs reported by $\geq 5\%$ of subjects in any treatment group)
- Related AEs by SOC and PT
- Related Grade 3 or higher AEs by SOC and PT.
- SAEs by SOC and PT
- Related SAEs by SOC and PT
- AEs leading to study drug discontinuation by SOC and PT
- AEs leading to study drug reduced by SOC and PT
- AEs leading to study drug held by SOC and PT
- Related AEs leading to study drug discontinuation by SOC and PT

- Related AEs leading to study drug reduced by SOC and PT
- Related AEs leading to study drug held by SOC and PT
- On-treatment death due to AE by SOC and PT, where on-treatment is defined as within 28 days of last dose.
- On-treatment death due to related AE by SOC and PT, where on-treatment is defined as within 28 days of last dose.

All AEs will be listed by subject. By-subject listings will be provided for AEs leading to on-treatment death, SAEs, and AEs leading to discontinuation of treatment.

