2.2. Secondary Objectives

The secondary objectives are:

- To evaluate the safety and tolerability of AG-120 compared to placebo.
- To evaluate PFS per Investigator assessment.
- To compare the efficacy of AG-120 with placebo based on overall survival (OS), objective response rate (ORR), duration of response (DOR), and time to response (TTR), with response assessed per the Investigator and by the IRC.
- To evaluate health-related quality of life (HRQOL) with AG-120 compared to placebo as assessed by the European Organization for Research and Treatment of Cancer Quality of Life Questionnaires (EORTC-QLQ-C30 and EORTC-QLQBIL21), the Patient Global Impression of Change (PGI-C), and the Patient Global Impression of Severity (PGI-S).
- To evaluate health economic outcomes as assessed by the 5-level EuroQol five dimensions questionnaire (EQ-5D-5L).
- To evaluate the pharmacokinetics (PK) of AG-120.
- To evaluate the PK/pharmacodynamic relationship of AG-120 and 2-hydroxyglutarate (2-HG) in blood samples.

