5. SAMPLE SIZE ESTIMATION

A total of approximately 186 subjects will be needed for the study.

The primary objective of the study is to demonstrate the improvement in PFS by IRC assessment for subjects receiving treatment with AG-120 as compared to subjects receiving placebo.

Assuming a hazard ratio (HR) of 0.5 for PFS (equivalent to a median PFS of 3 months in the placebo arm vs. 6 months in the AG-120 arm, assuming an exponential distribution), a total of 131 PFS events are required to provide 96% power at a 1-sided alpha of 0.025 level of significance to reject the null hypothesis using a stratified log-rank test. Based on this, a total of approximately 186 subjects will need to be randomized in a 2:1 ratio to the AG-120 and placebo arms, respectively, assuming approximately a 22% dropout rate, an approximate 26-month randomization period, and an additional 6-month follow-up for PFS after the last subject is randomized. Therefore, the primary analysis of PFS will occur at approximately 6 months after the last subject is randomized.

Overall survival will be analyzed twice, once at the time of the final analysis for PFS and once at the occurrence of 150 OS events (final analysis for OS, which will occur at approximately 24 months after the last subject is randomized). Assuming an HR of 0.67 for OS (median OS of 8 months in the placebo arm vs. 12 months in the AG-120 arm, assuming an exponential distribution), a total of 150 OS events will provide 64% power at a 1-sided alpha of 0.025.

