8. EFFICACY ANALYSIS

For PFS, best overall response (BOR), ORR, DOR and other endpoints based on progression and/or response status, the primary analyses will be based on the independent central review by IRC. The endpoints based on Investigator assessment will be used as secondary analyses. Efficacy data after crossover will be analyzed separately.

After unblinding at local PD per Investigator assessment, subjects on AG-120 are allowed to stay on AG-120 if the treating Investigator deems they are clinically benefiting. The IRC will read all scans up to the discontinuation of AG-120. Subjects on placebo will no longer stay on placebo after radiographic disease progression and unblinding, hence no further scans will be read by IRC beyond the initial locally assessed disease progression imaging time point. Because of that, there is a potential systematic bias that subjects on the AG-120 arm could have PD called by IRC later than the locally assessed PD date; however, subjects on the placebo arm would systematically be censored by IRC analysis at the time of local PD if not concordant with local PD. To alleviate the potential imbalance between two arms, IRC assessments after the local PD from both arms will be excluded from the primary analysis of scan-related endpoints per IRC read. A sensitivity analysis by including all the scans read by IRC will be conducted.

All efficacy analyses will be based on the ITT set unless stated otherwise. If analyses are performed on more than one analysis set, the analyses on the ITT set will be considered primary. For each period, once the PD occurred, or the new anticancer therapy was initiated, all the subsequent tumor/response assessments will not be included in the tumor/response related summary analyses, but it will be included in the data listings.

Data after crossover (such as PFS) will be analyzed in a similar manner.

Listings for all efficacy endpoints will be provided.

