10. GENERAL METHODS

Summary statistics will be presented by treatment and scheduled visit, unless stated otherwise.

Unless otherwise specified, descriptive statistics for continuous data will include the number of subjects with data to be summarized (n), mean, standard deviation, median, minimum, and maximum.

Descriptive statistics for categorical/qualitative data will include frequency counts and percentages. The total number of subjects in the treatment arm will be used as the denominator for percent calculations, unless stated otherwise.

Descriptive statistics associated with time-to-event analyses will include the number of events, the number of subjects censored, 25% quartile, median, 75% quartile, and 95% CI for median. These statistics will be presented for all time-to-event analyses, unless stated otherwise.

Listings will be provided for selected endpoints. Listings will be sorted by site, treatment, and subject IDs.

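### A cheap improvement to SAP 9.1: report person-time AE rates beside the crude incidences, because time at risk is expected to be longer on AG-120 than on placebo

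*SAP*

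**What the plan says.** The SAP's secondary objectives (2.2) include this one: "To evaluate the safety and tolerability of AG-120 compared to placebo". The AE plan in SAP 9.1 serves it with one kind of frequency measure: "Tables summarizing the incidence of AEs will be generated by treatment arms for each of the following". A treatment-emergent AE is one that starts or worsens from first dose "through 28 days after the last dose of study drug", and a subject counts once per preferred term. SAP 10 sets the default denominator: "The total number of subjects in the treatment arm will be used as the denominator for percent calculations". SAP 9 defines the safety columns: "it will include placebo before crossover, AG-120 as dosed, AG-120 after crossover, and total AG-120". Placebo AEs after crossover therefore leave the placebo column.

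Two other passages bear on time at risk. SAP 5 assumes a "median PFS of 3 months in the placebo arm vs. 6 months in the AG-120 arm". SAP 8 says that after unblinding at local progression "subjects on AG-120 are allowed to stay on AG-120 if the treating Investigator deems they are clinically benefiting", whereas placebo subjects do not stay on placebo.

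Protocol 12.9 and 12.9.1 are also based on incidence. Neither document plans a person-time AE rate or a common fixed window for AEs. Some related material exists:
- SAP 7.6 tabulates treatment duration by arm.
- SAP 9.2 summarises time to first QT prolongation AE.
- SAP 9.3 uses 30- and 60-day windows, for deaths only.
- Protocol 12.9.3 allows further safety analyses.

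**The concern.** Crude incidence depends on how long subjects are watched as well as on how often events happen. Three features of the plan lengthen AG-120 observation relative to placebo: longer assumed PFS, continuation after progression, and the cut of placebo data at crossover. For an AE that accrues at a steady background rate, the crude table mixes any drug effect with length of observation.

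SAP 8 recognises that continuation on AG-120 makes the arms unequal for central scan reads and adjusts the primary analysis for it. SAP 9 has no matching provision for AEs. What is at stake is interpretation: background or disease-related events could be read as effects of AG-120, and real signals are harder to pick out among them.

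**Working it through.** **Reproducing the plan's own figure.** With 131 events, HR 0.5, 2:1 allocation and one-sided 0.025, Schoenfeld power is Φ(√(131 × 2/9) × ln 2 − 1.96) = Φ(3.74 − 1.96) = 0.962. The plan states 96%, so its PFS assumptions are read correctly.

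**Inputs from the documents.** Exponential medians of 3 and 6 months (SAP 5), so λ = ln 2/3 = 0.231 and ln 2/6 = 0.116 per month. AE tail of 28 days: w = 28/30.4375 = 0.92 month (SAP 9.1). Accrual of 5 per month for 6 months, then 8 per month, to 186 (Protocol 7.1): 6 + (186 − 30)/8 = 25.5 months. Cutoff at about month 32 (Protocol 12.7.1). Arms of 62 and 124 (Protocol 8.1). Dropout: "assuming approximately a 22% dropout rate" (SAP 5).

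**Assumptions not in the documents.** Treatment time follows PFS. The AE hazard h is equal in both arms, so there is no drug effect. In the dropout case, dropout ends treatment at 0.04 per month in both arms. The fraction dropping out before progression is then 0.04/0.271 = 14.8% on placebo and 0.04/0.156 = 25.7% on AG-120. Weighted 1:2, that is 22%.

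**Closed form, without cutoff or dropout.** Mean time at risk = 1/λ + w: 4.33 + 0.92 = 5.25 months on placebo and 8.66 + 0.92 = 9.58 on AG-120. Crude incidence = 1 − exp(−hw) × λ/(λ + h). At h = 0.05 this is 1 − 0.955 × 0.822 = 21.5% on placebo and 1 − 0.955 × 0.698 = 33.3% on AG-120.

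**Simulation with accrual and the month-32 cutoff.** Mean time at risk is 5.0 vs 8.0 months, or 4.5 vs 6.6 with dropout. Crude incidence, placebo vs AG-120:

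| h per month | No dropout | Gap (points) | With dropout | Gap (points) |
|---|---|---|---|---|
| 0.01 | 4.8% vs 7.5% | 2.7 | 4.3% vs 6.3% | 2.0 |
| 0.02 | 9.3% vs 14.3% | 4.9 | 8.4% vs 12.0% | 3.6 |
| 0.05 | 20.9% vs 30.4% | 9.5 | 19.0% vs 26.2% | 7.2 |
| 0.10 | 35.8% vs 48.6% | 12.8 | 33.0% vs 43.0% | 10.0 |
| 0.5 | 80.0% vs 88.0% | 8.0 | 77.8% vs 84.9% | 7.2 |
| 1.0 | 92.5% vs 95.9% | 3.4 | 91.5% vs 94.6% | 3.1 |

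Gaps are taken before rounding. In every row the first-event rate per person-month is the same in both arms. For scale, the standard error of the crude difference with 62 and 124 subjects is 6.4-7.6 points at h = 0.05-0.10.

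**Crossover truncation.** Suppose 50-70% of placebo subjects cross over 0.25-0.5 month after last dose (assumed). The gaps at 0.05 and 0.10 widen to 10-11 and 14-16 points, or 8-9 and 11-13 with dropout.

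**Hazards that are not constant (equal in both arms, assumed; no dropout).**
- Month 1 only, 0.25 per month: crude 22.1% in both arms; rates 5.5 vs 3.5 per 100 person-months.
- 0.10 for 2 months, then 0.02: crude 21.9% vs 26.5%; rates 5.3 vs 4.3.
- Linked to progression, 0.02 on treatment and 0.3 in the 28-day tail: crude 29.1% vs 30.7%; rates 6.4 vs 4.4.

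In these three cases the crude figures are equal or tilt against AG-120, and the rates tilt in its favour.

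**The case against.** The strongest reply is that crude on-treatment incidence answers a legitimate question: the chance of an event during treatment as given. The tables are descriptive, exposure is reported by arm, every AE is listed by subject, and further safety analyses are allowed. This stands as a reason not to call the plan wrong. However, none of these items adjusts an AE figure, and the permission for further analyses is unspecified.

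The size is also not established. Complications of progression are reportable AEs (Protocol 11.1.1) and can fall in the 28-day tail. In that case the crude gap nearly vanishes, and a person-time rate carries a bias of its own, towards AG-120. This stands too. It is why rates should sit beside the percentages and not replace them.

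A reader might infer that AEs will look more frequent on AG-120 by some fixed amount. The documents do not support that. They give PFS medians, but no treatment durations and no AE time profiles for this trial, and the cases above run from 0 to about 16 points.

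A reader might also infer that SAP 9.2 mishandles QT prolongation by summarising onset only among subjects with an event. Its wording (a continuous summary plus day bands) is open to that reading. But SAP 10 sets numbers censored and quartiles as the default for time-to-event analyses, and Protocol 12.1 prescribes Kaplan-Meier for time-to-event endpoints. All that is left is a clarification.

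**Conclusion.** The point holds as a cheap improvement, not as an error in the plan. No planned analysis of AE frequency in SAP 9.1 accounts for time at risk, and the plan's own assumptions imply about 1.5 to 1.6 times as much of it on AG-120 (6.6/4.5 to 8.0/5.0).

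With equal hazards, the spurious crude gap is:
- 0 points for AEs confined to month 1, and under 2 points in the progression-linked case;
- 2-5 points at 0.01-0.02 per month;
- 7-13 points at 0.05-0.10 per month, and up to about 16 with crossover truncation;
- 3-8 points (ratio 1.03-1.10) for very common AEs.

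All of these figures rest on treatment time following PFS and on the assumed hazards. Continuation of AG-120 after progression is not in the simulation and would widen the gaps for steadily accruing AEs. No type I error rate, power or sample size is affected, and the crude distortion makes AG-120 look worse, not safer.

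**What to change.** In SAP 9.1, keep the crude percentages. For all AEs, Grade 3 or higher AEs and SAEs, by SOC and PT, add first events per 100 person-months at risk by arm. Time at risk ends at the first event, last dose plus 28 days, crossover or data cutoff, whichever comes first.

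Footnote two things. The crude percentages are not adjusted for exposure. The rates assume a roughly constant hazard and can favour AG-120 for AEs that come early or are linked to progression, so the two must be read together.

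In SAP 9.2, state that time to first QT prolongation AE follows the Kaplan-Meier rule of Protocol 12.1 and the time-to-event defaults of SAP 10, with subjects without an event censored at the end of the same window.

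The cost is a little more analysis work. First dose, last dose and crossover dates are already in the SAP 7.1 listing, and AE onset dates are collected under Protocol 11.2. The remaining downside is that the added rates carry their own bias when the hazard is not constant. The QT curve will also be imprecise late on: about 16-19 of 62 placebo subjects are expected to be at risk at 6 months under the same assumptions.

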9.2. Adverse Events of Special Interest

QT prolongation AEs will be summarized for the following:

- a) QT prolongation all grades by PT
- b) QT prolongation Grade 3 or higher by PT
- c) Treatment-related QT prolongation all grades by PT

Time to first QT prolongation AE will be summarized continuously and by ≤ 15 days, 16-30, 31-45, 46-60, and >60 days for all grade and Grade 2 or higher AEs.

9.3. On-Treatment Death

All on-treatment deaths (≤ 28 days of last dose) and the reason of deaths will be summarized by treatment based on SAS set.

In addition, all-cause mortality will be summarized including the deaths ≤ 30 days of the first and last dose, and ≤ 60 days of the first and last dose.

9.4. Laboratory Data

Unless specified otherwise, lab data will be summarized by treatment and scheduled visits. Data after crossover will be summarized by scheduled visits in a separate table or listing. The baseline used in the “after crossover” outputs will be the closest assessment prior to subjects receive open-label AG-120.

9.4.1. Hematology

For hematologic parameters, the actual values and the change from baseline will be summarized by treatment and scheduled visits.

Shift tables will be presented based on CTCAE grade by treatment, including

- WBC (low)
- Absolute Neutrophil Count (low)
- Hgb (low)
- Platelets (low)

9.4.2. Clinical Chemistry

For chemistry parameters, the actual values and the change from baseline will be summarized by treatment and scheduled visits.

Shift tables from baseline to worst value based on CTCAE grade will be presented by treatment, including

- Bilirubin (high)
- Alkaline Phosphatase (high)
- ALT (high)
- AST (high)
- Sodium (low)
- Potassium (low/high)
- Phosphate (low)

In addition, subjects with liver dysfunction will be presented in a listing. Liver dysfunction is defined as elevated ALT or AST of $\geq 3x$ ULN and associated with increase in total bilirubin $\geq 2x$ ULN (± 10 days).

9.4.3. CA19-9 Level

The actual values and the change from baseline for CA19-9 level will be summarized by treatment arm and scheduled visits. A corresponding data listing will be provided.

9.4.4. Coagulation Analysis

The following coagulation tests will be presented in a listing: prothrombin time (PT), activated partial thromboplastin time (aPTT), and international normalized ratio (INR).

9.4.5. Urinalysis

Urinalysis results will be listed.

9.4.6. Pregnancy Tests

The pregnancy test results will be listed.

9.5. Physical Examination

A by-subject listing will be presented for any clinically significant findings from physical examination.

9.6. Vital Signs

Vital signs (except height) will be presented as both actual values and changes from baseline by treatment and scheduled visits. Vital sign measurements will also be listed.

9.7. Electrocardiograms (ECGs)

Descriptive statistics for the actual values and changes from baseline over time will be summarized for each ECG parameter: QT (msec), RR interval (msec) and QTcF (Fridericia's correction). QTcF is calculated as $QTcF = QT / \text{cube root of RR interval}$.

The proportion of subjects with maximum post-baseline absolute QTcF intervals that fall into following categories will be presented:

- ≤ 450 msec
- >450 and ≤ 480 msec
- >480 to ≤ 500 msec
- >500 msec

The proportion of subjects who have a maximum post-baseline change from baseline in QTcF intervals of the following categories will be presented:

- ≤ 0 msec
- >0 to ≤ 30 msec
- >30 to ≤ 60 msec
- >60 msec

A listing of subject-level ECG measurement will be provided.

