9.9. Guidelines for Management of QT Prolongation

The discussion of the emergency management of Torsades de pointes and its hemodynamic consequences is beyond the scope of this guideline.

Events of QTcF prolongation \geq Grade 2 should be reported as AEs of special interest (AESIs) to the Sponsor within 24 hours, according to expedited reporting procedures (see Section 11.2.3).

The following are guidelines for the management of AEs of special interest based on the AG-120 non-clinical and clinical safety findings in subjects with solid tumors to date.

Prolongation of QTcF interval has been observed in monkeys at relatively high doses of AG-120 (see Section 5.3.2.2) and has been identified as an expected risk of treatment with AG-120 (see the Investigator's Brochure). As of 16 January 2016, 12 (10%) of 122 subjects in Study AG120-C-002 and 19 (16%) of 119 subjects in Study AG120-C-001 have experienced QT prolongation while receiving AG-120.

Subjects may be at increased risk for the development of QT prolongation when treated with AG-120 in combination with fluoroquinolones, azole antifungal agents, or serotonin (5-HT₃) antagonists. Investigators need to be vigilant; refrain from administering concomitant medications associated with QT prolongation and if no other therapeutic options are available, monitor subjects receiving study treatment with the combination of these drugs, and evaluate ECG and electrolytes (including potassium, magnesium, and calcium) particularly in subjects presenting with nausea, vomiting, or diarrhea. Systemic administration of a moderate or strong CYP3A4 inhibitor requires careful monitoring of QTcF (see Section 9.13.2).

Subjects who experience prolongation of the QTcF interval to >480 msec (CTCAE Grade ≥ 2) while receiving study treatment, should be promptly evaluated for causality of the QTcF prolongation and managed according to the following guidelines and Table 2:

- Levels of electrolytes (potassium, calcium, and magnesium) should be checked and supplementation given to correct any values outside the normal range.
- Concomitant therapies should be reviewed and adjusted as appropriate for medications with known QT prolonging effects.

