- If no other cause is identified and the Investigator believes it is appropriate, particularly if QTcF remains elevated (after above measures have been implemented, or as determined by the Investigator), study treatment may be interrupted, and an ECG should be rechecked in approximately 1 week after the QTcF prolongation was

first observed or more frequently as clinically indicated. If QTcF has recovered or improved and the Investigator believes it is safe to do so, re-challenge with study treatment should be considered if held.

- ECGs should be conducted at least weekly (eg, at every scheduled visit) for 2 weeks following QTcF reduction ≤ 480 msec.

Table 2: Management of QT Prolongation by CTCAE Grade

CTCAE Grade	Management
Grade 2 (QTcF >480 and ≤ 500 msec)	
 • The dose of study treatment may be reduced to 250 mg QD without interruption of dosing. The dose of study treatment may be re-escalated to the prior dose in ≥ 14 days after QT prolongation has decreased to \leq Grade 1.
Grade 3 (QTcF >500 msec on at least two separate ECGs)	
 • Hospitalization for continuous cardiac monitoring and evaluation by a cardiologist should both be considered. • Dosing with study treatment will be interrupted. If QTcF returns to within 30 msec of baseline or <450 msec for males and <470 msec for females within 14 days, treatment may be resumed at a reduced dose of 250 mg. • The dose of study treatment cannot be re-escalated following dose reduction for Grade 3 QTcF prolongation unless the prolongation was associated with an electrolyte abnormality or concomitant medication.
Grade 4 (QTcF >500 msec or >60 msec change from baseline with Torsades de pointes or polymorphic ventricular tachycardia or signs/symptoms of serious arrhythmia)	
 • Subjects should be admitted to a hospital for continuous cardiac monitoring and discharged only after review by a cardiologist. • Dosing with study treatment should be permanently discontinued.

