13.5. Protocol Compliance

The Investigator will conduct the study in compliance with the protocol. Modifications to the protocol should not be made without agreement of both the Investigator and the Sponsor. Changes to the protocol will require written IRB/IEC approval/favorable opinion prior to implementation, except when the modification is needed to eliminate an immediate hazard(s) to subjects. The IRB/IEC may provide, if applicable, where regulatory authority(ies) permit, expedited review and approval/favorable opinion for minor change(s) in ongoing studies that have the approval/favorable opinion of the IRB/IEC. The Sponsor or designee will submit all protocol modifications to the regulatory authority(ies) in accordance with the governing regulations.

When immediate deviation from the protocol is required to eliminate an immediate hazard(s) to subjects, the Investigator will contact the Sponsor or Medical Monitor, if circumstances permit, to discuss the planned course of action. Any departures from the protocol must be fully documented in the source documents/eCRF.

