1. INTRODUCTION

This statistical analysis plan (SAP) describes the analysis for Protocol AG-120-C-005, “A Phase 3, Multicenter, Randomized, Double-Blind, Placebo-Controlled Study of AG-120 in Previously Treated Subjects with Nonresectable or Metastatic Cholangiocarcinoma with an IDH1 Mutation,” Amendment 4, Version 5.0, which was issued on 04 April 2018. It contains definitions of analysis populations, derived variables, and statistical methods for the analysis of efficacy and safety.

This SAP provides a comprehensive and detailed description of the strategy, rationale, and statistical techniques to evaluate the necessary efficacy and safety endpoints. The purpose of this SAP is to ensure the credibility of the study findings by pre-specifying the statistical approaches to the analysis of study data prior to database lock. Pharmacokinetic (PK)/pharmacodynamic analysis and exploratory biomarker analyses are not in the scope of this SAP. This SAP will be finalized and approved prior to the database lock for the primary analysis.

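### Does the QTcF formula in SAP 9.7, printed without a unit for RR, put the QTcF tables on the wrong scale?

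*SAP*

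**What the plan says.** SAP section 9.7 plans descriptive statistics for actual values and changes over time, "summarized for each ECG parameter: QT (msec), RR interval (msec) and QTcF". The sentence after that gives the derivation: QT over the "cube root of RR interval", under the name of Fridericia's correction. It gives no unit for RR and no conversion.

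The section then sorts each subject's maximum post-baseline QTcF at 450, 480 and 500 msec, and the maximum change from baseline at 0, 30 and 60 msec. It closes with "A listing of subject-level ECG measurement will be provided".

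Protocol Appendix 15.4 prints the same formula, also without units. Elsewhere the protocol uses QTcF on the ordinary millisecond scale:

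- Exclusion criterion 15 applies from 450 msec.
- Section 9.9 addresses subjects who "experience prolongation of the QTcF interval to >480 msec".
- Table 2 defines Grade 3 as "QTcF >500 msec on at least two separate ECGs".

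**The concern.** A derivation rule in an SAP should give the right number when it is applied with the units printed next to it. Here the unit next to it is milliseconds, while the formula gives QTcF on the scale of the section's categories only when RR is in seconds. Read literally with RR in milliseconds, the rule would push every realistic absolute value into the lowest category and all but empty the two upper change categories. The tables would then suggest that no subject had a prolonged interval.

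The parameter is not incidental. Protocol section 5.4 names prolonged QT as the only expected risk in solid tumors. Protocol section 11.2.3.1 makes Grade 2 or worse prolongation a reportable event of special interest. Protocol section 9.9 reports QT prolongation in 12 of 122 subjects (10%) in the earlier solid-tumor study. An empty upper category in the measured-QTcF tables would be a misleading safety result.

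**Working it through.** The plan prints no worked QTcF value, so there is no figure to reproduce. The check is one of units.

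**Inputs.** QT and RR in msec, the formula, and the category limits are all from SAP 9.7. The QT and RR values below are illustrative assumptions; the documents give none.

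**Step 1: size of the discrepancy.** With RR recorded in msec,

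- RR converted to seconds: QTcF = QT / (RR/1000)^(1/3)
- RR left in msec: QTcF = QT / RR^(1/3)

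The ratio of the first to the second is 1000^(1/3) = 10 for every QT and RR. A change is a difference of two such values, so it is also reduced by exactly 10.

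**Step 2: examples.**

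| QT (msec) | RR (msec) | QTcF, RR in seconds | QTcF, RR in msec |
|---|---|---|---|
| 400 | 1000 | 400.0 | 40.0 |
| 400 | 800 | 430.9 | 43.1 |
| 440 | 1200 | 414.1 | 41.4 |
| 480 | 1000 | 480.0 | 48.0 |
| 520 | 1000 | 520.0 | 52.0 |

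For a change from QT/RR 400/900 to 470/800, RR in seconds gives 506.3 − 414.3 = +92.0 msec. RR in msec gives 50.6 − 41.4 = +9.2.

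**Step 3: which reading fits the section's categories.** With RR in msec at RR 1000, exceeding 450 needs QT above 450 × 10 = 4500 msec. At that constant RR, a change above 30 needs a QT change above 30 × 10 = 300 msec, and a change above 60 needs one above 60 × 10 = 600 msec. Categories that almost nobody could enter cannot be what was meant. With RR in seconds, the examples spread across the limits as expected. The protocol limits of 450, 480 and 500 msec point the same way.

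**Step 4: what the slip would do.** Not every cell would be wrong. Subjects truly at or below 450 msec stay in the lowest category. Changes at or below 0 keep their sign and their category, and true changes above 0 up to 30 stay in theirs. The loss is in the higher categories, whose members would drop to a lower one.

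**Step 5: would it be seen?** For an assumed RR of 500 to 1200 msec (120 to 50 beats/min), the divisor in seconds runs from 0.794 to 1.063. QTcF is then between 1/1.063 = 0.94 and 1/0.794 = 1.26 times QT. In msec the divisor runs from 7.94 to 10.63, so QTcF is between 0.094 and 0.126 times QT. SAP 9.7 places QT and QTcF in the same descriptive summary and also provides the subject-level listing. A mean QTcF about one tenth of the mean QT, in a trial whose eligibility limit is 450 msec, would be plain in the first draft output.

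**Step 6: reach.** SAP 9.2 summarizes QT events from reported adverse events ("QT prolongation AEs will be summarized for the following"), not from this formula. Site management under Protocol section 9.9 does not use the SAP derivation. No efficacy endpoint uses QTcF.

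**The case for a change.** The best case for an edit is that neither document says seconds, that SAP 9.7 says QTcF is calculated (so one cannot assume it is copied from the ECG record), and that likely detection does not repair a written rule. The edit would also be cheap. It is one line in a document of which the introduction says "This SAP will be finalized and approved prior to the database lock for the primary analysis", and it would avoid the protocol route, where "Changes to the protocol will require written IRB/IEC approval/favorable opinion prior to implementation".

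The factual part stands: the RR unit is unstated in the formula, and the factor of ten is exact. What does not follow is that the plan contains an arithmetic error. The millisecond label describes how RR is displayed in the summaries; the formula is a separate sentence without a unit, and nothing tells the analyst to carry the label into it. Protocol Appendix 15.4 prints the same bare formula and causes no difficulty. Low cost is not a reason by itself when the edit would leave every table that a competent programmer produces exactly as it would have been.

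**Conclusion.** No change is needed. SAP 9.7 omits the RR unit from its QTcF formula, but the named correction and the section's own millisecond categories allow only RR in seconds. Analysts will convert RR to seconds, that is, QTcF (msec) = QT (msec) / (RR (msec)/1000)^(1/3).

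The tenfold error is real only under a reading that the section itself rules out. It would be confined to the QTcF descriptive and categorical tables and would be obvious beside the QT values. If section 9.7 is reopened for another reason, the unit can be printed then, as an editorial courtesy.

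This rests on two assumptions: that the programmers know the usual Fridericia convention or compare their output with the categories, and that someone reads the QTcF summary beside the QT summary. Both are ordinary practice.
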